6.2. Analysis Plan of Secondary Endpoints

6.2.1. SDAI remission rate at Week 24

SDAI remission rate at Week 24 and its two-tailed 95% confidence interval will be calculated for each ARM (ARM-1, 2, and 3).

6.2.2. SDAI remission rate at Week 48 in MTX monotherapy groupSDAI remission rate at Week 48 and its two-tailed 95% confidence interval in MTXMonotherapy Group (ARM-1) will be calculated.

6.2.3. ACR20, ACR50, and ACR70 response rate at each assessment timepoint ACR20, ACR50, and ACR70 response rates and their two-tailed 95% confidence interval at each assessment timepoint will be calculated for each ARM (ARM-1, 2, and 3). Furthermore, Mantel-Haenszel test (risk difference) with country as a stratification factor will be performed to compare response rates at Week 48 between ARM-2 and ARM-3, and calculate the estimate of difference between the treatment arms and its two-tailed 95% confidence interval.

As a sensitivity analysis, point estimates and their 95% confidence interval for changes in ACR20, ACR50, and ACR70 response rates from baseline to each assessment timepoint will be calculated by generalized linear mixed model (Breslow NE, Clayton DG, J Am Stat Assoc 1993;88(421): 9-25, Wolfinger RD, O'Connell MA, J Stat Comput Sim 1993; 48: 233-243.). Unstructured will be selected as a correlation structure, and if the analysis does not converge, Toeplitz, Autoregressive, Compound-symmetry structure will be used in order.

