## 0.5 Study treatment

Study treatment will start with MTX 6 to 8 mg/week, which will be promptly escalated to the maximum tolerable dose (MTD)  $\leq$ 25 mg/week (the maximum dose should be set according to the package insert of each country) in line with EULAR Recommendations 2016, and will be in principle maintained at the MTD from Week 12 onward. Also, the dosage of MTX will remain unchanged from Week 20 to 24 except for dose reduction/interruption due to an adverse drug reaction (ADR).

If the dosage of MTX is maintained  $\geq 10$  mg/week and remission (SDAI  $\leq 3.3$ ) is achieved at Week 24, the MTX therapy will be continued (ARM-1).

If SDAI remission is not achieved despite the dosage of MTX is maintained  $\geq 10$  mg/week at Week 24, a bDMARDs will be added to the treatment in line with EULAR Recommendations 2016. Subjects will subcutaneously receive ADA 40 mg as a bDMARD every other week up to Week 48, and be randomized to a group in which the MTD of MTX (10 to 25 mg/week) will be maintained (ARM-2) and a group in which the dosage of MTX will be reduced to 6 to 8 mg/week (ARM-3). Then, the efficacy and safety will be evaluated. If a subject becomes intolerable to MTX  $\geq 10$  mg/week at Week 24 due to an ADR or other relevant reasons, the subject will be terminated from the study at that time. The subject will

be also terminated from the study when subjects have received a non-ADA bDMARD or JAK inhibitor.

The primary endpoint will be the SDAI remission rate at Week 48 in the ADA/MTX-MTD Group (ARM-2) and ADA/MTX-Reduced Dose Group (ARM-3). Key secondary endpoints will be the SDAI remission rate at Week 24, the SDAI remission rate at Week 48 in MTX Monotherapy Group, the modified total sharp score (mTSS) at each assessment timepoint and changes from baseline to each assessment timepoint, and ACR20, ACR50, and ACR70 response rates at each assessment timepoint. Also, the correlation of the erythrocyte MTX-PG concentration to SDAI, mTSS, and ACR-N will be exploratorily evaluated.

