## 4.1.2 Secondary endpoints

- SDAI remission rate at Week 24
- SDAI remission rate at Week 48 in MTX Monotherapy Group

- ACR20, ACR50, and ACR70 response rate at each assessment timepoint
- HAQ remission rate at each assessment timepoint
- SDAI, CDAI, DAS28-ESR, and DAS28-CRP at each assessment timepoint, and change from baseline to each assessment timepoint
- Tender joint count, swollen joint count, VAS (physician- and patient-reported), HAQ, CRP, ESR, MMP-3, RF, and anti-CCP antibody at each assessment timepoint, and change from baseline to each assessment timepoint
- Modified total sharp score (mTSS) at each assessment timepoint, and change from baseline to each assessment timepoint
- Structural remission (mTSS  $\leq 0.5$ ) rate at each assessment timepoint
- Vital signs and laboratory findings at each assessment timepoint, and change from baseline to each assessment timepoint
- Status of AE (Up to Week 24, and up to Week 48 for each ARM)

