## 4.3 Bias

#### 4.3.1 Randomization

If a subject does not achieve to clinical remission (SDAI  $\leq$ 3.3) at Week 24 despite the maintenance of MTX dose at  $\geq$ 10 mg/week, the subject will start receiving ADA as an add-on therapy. Subjects then will be stratified by countries (Japan, South Korea, and Taiwan) as a stratification factor, and for each stratum, subjects will be randomized at a 1:1 ratio to either a group in which the MTD of MTX (10 to 25 mg/week) will be maintained (ARM-2), and a group in which the dosage of MTX will be reduced to 6 to 8 mg/week (ARM-3). Upon completion of Week 24 assessments, principal investigator/sub-investigator shall enter the Week 24 dosage of MTX, tender joint count (28 joints), swollen joint count (28 joints), VAS (physician- and patient-reported; 10 cm scale), and CRP in IWRS. If all necessary information is entered, a relevant treatment group in line with the status of randomization (ARM-1, ARM-2 or ARM-3) will be issued by IWRS.

The MTX dosage shall be either 6 mg/week or 7.5 mg/week in subjects in ARM-3 whose maintenance dose of MTX at Week 24 is 10 mg/week.

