## 9.2.1.2 Method of analysis for secondary efficacy endpoints

SDAI remission rate at Week 24, SDAI remission rate at Week 48 in MTX Monotherapy Group (ARM-1), ACR20, ACR50, and ACR70 response rates, HAQ remission rate, and structural remission rate at each assessment timepoint, and their two-tailed 95% confidence intervals will be calculated for each ARM. Furthermore, ARM-2 and ARM-3 at Week 48 will be compared using a stratified analysis with country as a factor.

Summary statistics (mean, standard deviation, median, and range) in each ARM at each assessment timepoint will be calculated for SDAI, CDAI, DAS28-ESR, DAS28-CRP, tender joint count, swollen joint count, VAS (physician- and patient-reported), HAQ, CRP, ESR, MMP-3, RF, anti-CCP antibody, and mTSS, and their changes from baseline to each assessment timepoint. For mTSS at Week 48, changes from Week 24 will also be analyzed for the summary statistics. In addition, ARM-2 and ARM-3 will be compared in terms of changes from Week24 to Week 48 using a stratified analysis with country as a factor.

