## 9.7 Data evaluation

Prior to the final analysis, the data obtained before randomization will be summarized in the course of the study for the purpose of presentations at academic conferences. The summary of the data are allowed to be presented at academic conferences after the completion of subject enrollment in principle. This study will not be biased as the data obtained before randomization are collected.

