2.1. Data Evaluation

The interim analysis will not be conducted in this study. However, prior to the final analysis, the data obtained before randomization will be summarized in the course of the study for the purpose of presentations at academic conferences. The summary of the data is allowed to be presented at academic conferences after the completion of subject enrollment in principle. This study will not be biased as the data obtained before randomization are collected.

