4.1. Subject Disposition

The following numbers will be calculated: Number of subjects enrolled; number of subjects who received the study drug (MTX), number of subjects with evaluable/non-evaluable SDAI at Week 24; number of subjects included in the Safety Analysis Set; number of subjects included in FAS. In addition, the following numbers will also be calculated: Number of subjects who withdrew the informed consent; number of subjects who had not received any study drug after enrollment, number of subjects without any data on the primary endpoint; number of subjects who did not meet the inclusion criteria; number of subjects who met the exclusion criteria.

Of subjects who satisfied the criteria for SDAI remission at Week 24 and were randomized to ARM-1, the number of subjects who did/did not have SDAI remission at Week 48, number of subjects included in the Safety Analysis Set, and number of subjects included in FAS will be calculated. Furthermore, the number of subjects who had not received any study drug after Week 24, and number of subjects without any data on the primary endpoint at Week 24 onward will also be calculated.

Of subjects who did not achieve SDAI remission at Week 24, the following numbers will be calculated for ARM-2 and ARM-3, respectively: Number of subjects randomized; number of subjects who did/did not achieve SDAI remission at Week 48; number of subjects included in the Safety Analysis Set, FAS, mFAS, and PPS, respectively. In addition, the number of subjects who had not received any study drug after randomization, and number of subjects without any data on the primary endpoint after randomization, will also be calculated.

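### The Week 24 SDAI remission rate is planned only by ARM, where it is 100%, 0% and 0% by construction; no FAS-wide rate is specified, and the mixed-model sensitivity analysis leaves its arm contrast unstated

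*SAP*

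**What the plan says.** Protocol 0.5 puts this endpoint first among the key secondaries: "Key secondary endpoints will be the SDAI remission rate at Week 24". Protocol 4.1.2 and SAP 1.2 list it with no restriction to an ARM. The next item in both lists is restricted; in the protocol it reads "SDAI remission rate at Week 48 in MTX Monotherapy Group".

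The analysis sections then split the Week 24 rate by ARM. SAP 6.2.1 says "SDAI remission rate at Week 24 and its two-tailed 95% confidence interval will be calculated for each ARM (ARM-1, 2, and 3"). In Protocol 9.2.1.2 a sentence that opens with this rate ends "and their two-tailed 95% confidence intervals will be calculated for each ARM".

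The ARM depends on Week 24 remission. Protocol 4.3.1 begins the route to ARM-2 or ARM-3 with "If a subject does not achieve to clinical remission", and SAP 4.1 describes ARM-1 as "Of subjects who satisfied the criteria for SDAI remission at Week 24 and were randomized to ARM-1". Under Protocol 6.1, subjects who cannot hold MTX at 10 mg/week or more at Week 24 are withdrawn, so they get no ARM. SAP 3.2 assigns secondary efficacy to the FAS, and SAP 3.1.1 expressly keeps those who stopped before Week 24 in it.

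For the primary endpoint, SAP 6.1 first defines a Mantel-Haenszel risk difference with a 90% CI and a margin of -15%. It then adds a generalized linear mixed model as a sensitivity analysis. The stated output of that model is the change in remission rate since baseline at each visit, with a 95% CI.

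SAP 6.2.6 plans ARM-2 versus ARM-3 comparisons of remission and low disease activity at every visit for four indices.

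**The concern.** A rate tabulated within groups that were formed on that same outcome carries no information about the outcome. The Week 24 rate is the study's estimate of how often MTX alone brings these patients to remission, and it is the quantity assumed to be 15% when enrolment was set. As specified, the table would not estimate it. The subjects for whom MTX monotherapy failed early or was not tolerated would be absent, although they belong to the declared analysis set.

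The mixed-model point is smaller. A sensitivity analysis of a non-inferiority result should yield the same contrast as the primary analysis, so that the two can be compared. A change since baseline is not that contrast.

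**Working it through.** **1. What the ARM rule implies at Week 24** (Protocol 4.3.1 and 6.1, SAP 4.1)

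| Status at Week 24 | Assignment | SDAI remission in the by-ARM table |
|---|---|---|
| SDAI at most 3.3, MTX at least 10 mg/week | ARM-1 | 100% |
| SDAI above 3.3, MTX at least 10 mg/week | ARM-2 or ARM-3, 1:1 | 0% in each |
| MTX of 10 mg/week not maintained | withdrawn | not shown |
| Stopped before Week 24 | none | not shown |

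**2. The plan's own figure.** Protocol 9.4.1 needs 220 randomised, with 15% remission on MTX alone and 10% unable to continue 10 mg/week. 220 / (0.85 x 0.90) = 287.6, rounded up to 288. This matches the stated 288, so the overall Week 24 rate is a planning input.

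**3. The by-ARM output at 300 enrolled.** 300 x 0.90 = 270 receive an ARM and 30 do not. 270 x 0.15 = 40.5 go to ARM-1. The other 229.5 are randomised, about 115 per arm. Exact (Clopper-Pearson) 95% intervals:
- ARM-1: 40/40 = 100%; lower limit 0.025^(1/40) = 91.2%.
- ARM-2 and ARM-3: 0/115 = 0% each; upper limit 1 - 0.025^(1/115) = 3.2%.

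These limits depend only on arm size.

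**4. The whole-FAS rate** (FAS assumed to be about 300)
- None of the 30 without an ARM is observed in remission: 40/300 = 13.3% (9.7 to 17.7).
- 15% of those 30 are (4.5, assumed): 40.5 + 4.5 = 45; 45/300 = 15.0% (11.2 to 19.6).
- Across the source rates quoted in Protocol 9.4.1 (11.2% to 29.3%): from 34/300 (95% CI 8.0 to 15.5) to 88/300 (24.2 to 34.8).

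The first two lines differ only in how the subjects without an ARM are counted, which the plan does not settle for an overall rate.

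**5. The mixed model.** Baseline remission is close to 0, because entry requires SDAI above 11 (Protocol 5.1). Week 24 remission is 0 in both randomised arms by design. As an illustration, a plain logistic fit was run on simulated data for 220 subjects, with remission assumed at 25% at Week 36 and 30% at Week 48. In the all-zero cells the coefficients were about -26.6 with standard errors near 34,000. At Weeks 36 and 48 the standard errors were about 0.2. On a logit scale, change since baseline is therefore not estimable, while the Week 48 arm contrast is.

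At the planned 30% in both arms with 110 per arm, SE = sqrt(2 x 0.30 x 0.70 / 110) = 0.0618 and 1.645 x 0.0618 = 0.102. The contrast is 0 with a 90% CI of -10.2 to +10.2 points, which can be read against -15. The output as worded, if given by arm, would be two changes of +30 points (95% CI 21.4 to 38.6 each) and no verdict.

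**6. SAP 6.2.6.** At Week 24, SDAI remission in ARM-2 versus ARM-3 is 0 versus 0, with no variance. By Protocol 7.2.4 and 7.2.5, SDAI equals CDAI plus CRP. A subject with SDAI above 3.3 can have CDAI of 2.8 or less only if CRP exceeds 3.3 - 2.8 = 0.5. CDAI remission at Week 24 is therefore restricted by the same selection.

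**The case against.** **The Week 24 rate can be rebuilt.** SAP 4.1 already counts the FAS, Week 24 SDAI evaluability and the subjects in ARM-1, and SAP 2.4 has a non-responder rule. SAP 2.1 adds that "the data obtained before randomization will be summarized in the course of the study for the purpose of presentations at academic conferences", and Protocol 9.7 says the same. The endpoint is descriptive, with no hypothesis attached. This largely stands, and a reader who inferred that the overall rate will be unobtainable would go too far. But ARM-1 over FAS misses remitters below 10 mg/week, and the conference summary names no endpoint, denominator or interval. The result is an approximation, not a specified analysis.

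**The mixed-model sentence takes its meaning from its section.** It sits under the primary endpoint. SAP 3.2 and 4.3 fix that endpoint's analysis sets as mFAS and PPS, and mFAS contains only ARM-2 and ARM-3. SAP 2.4 treats missing remission as non-response and prescribes GEE or MMRM, then LOCF, for missing scores. The End of Study sentence in SAP 6.1 is equally terse. If results came out by arm, a reader could subtract them. Most of this stands: an arm comparison is probably intended, and it would be wrong to infer that no analysis set or missing-data rule exists. What remains is that the contrast, the 90% level, the margin and the link are not written for this model, and that SAP 2.4 and 6.1 are not harmonised. Reporting 95% instead of 90% could only under-claim non-inferiority.

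**Conclusion.** The by-ARM analysis of the Week 24 SDAI remission rate is wrong as written. It returns 100%, 0% and 0% by construction and leaves out FAS subjects without an ARM. This assumes that the SDAI used for analysis agrees with the values entered at randomisation; corrections or misallocation could move it slightly. The estimate of about 13% to 15% rests on the plan's 300, 10% and 15%, and on a FAS of about 300.

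The unstated contrast in the mixed model is a secondary gap in wording, and the Week 24 comparisons in SAP 6.2.6 are minor.

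A reader might infer that the non-inferiority conclusion is at risk, because withdrawal could differ by arm. The documents do not support this. Assume 110 per arm with 33 observed remitters in ARM-2 and 29 in ARM-3. The primary rule then gives -3.6 points with a 90% lower limit of -13.6. Unstratified complete-case lower limits are -11.7, -14.7 or -17.9 if 5/15, 10/10 or 15/5 subjects are missing in ARM-2/ARM-3. Only the last crosses -15. Every count is assumed, and the plan does not say which arm would lose more subjects. The Mantel-Haenszel primary analysis is unaffected.

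**What to change.** 1. **SAP 6.2.1 and Protocol 9.2.1.2:** replace the by-ARM Week 24 analysis with one SDAI remission rate and 95% CI in the whole FAS, optionally by country. Count missing as non-responder under SAP 2.4, and count observed remitters below 10 mg/week as observed.
2. **SAP 6.1:** state that in mFAS the mixed model estimates the Week 48 ARM-3 minus ARM-2 risk difference with a 90% CI against -15%, adjusted for country. Name the link, use post-randomisation visits only (Weeks 36 and 48), and leave missing remission as missing. Setting it to non-response would merely repeat the primary rule. Reconcile this with the GEE, MMRM and LOCF text in SAP 2.4. The same change-from-baseline wording recurs in SAP 6.2.3 to 6.2.5 and should be checked with it.
3. **SAP 6.2.6:** limit the ARM-2 versus ARM-3 comparisons to post-randomisation visits.

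The cost is some wording and programming, with no new data and no change to the primary analysis. The one drawback is a second 90% CI that may differ from the primary result and would need explaining. A simulation of item 2 assumed 110 per arm, remission of 25% and 30% at Weeks 36 and 48, latent correlation 0.6, 8% missing at Week 48 and a 60/20/20 country split. The model converged in 300 of 300 data sets with a logit link and in 300 of 300 with an identity link. Mean 90% CI widths were 21.0 and 20.9 points, against 19.6 and 19.7 for Mantel-Haenszel.

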6.2.4. HAQ remission rate at each assessment timepoint

HAQ remission rate and its two-tailed 95% confidence interval at each assessment timepoint will be calculated for each ARM (ARM-1, 2, and 3). Furthermore, Mantel-Haenszel test (risk difference) with country as a stratification factor will be performed to compare HAQ remission rates at Week 48 between ARM-2 and ARM-3, and calculate the estimate of difference between the treatment arms and its two-tailed 95% confidence interval.

As a sensitivity analysis, point estimates and their 95% confidence interval for changes in

HAQ remission rate from baseline to each assessment timepoint will be calculated by generalized linear mixed model (Breslow NE, Clayton DG, J Am Stat Assoc 1993;88(421): 9-25, Wolfinger RD, O'Connell MA, J Stat Comput Sim 1993; 48: 233-243.). Unstructured will be selected as a correlation structure, and if the analysis does not converge, Toeplitz, Autoregressive, Compound-symmetry structure will be used in order.

6.2.5. SDAI, CDAI, DAS28-ESR, and DAS28-CRP at each assessment timepoint, and change from baseline to each assessment timepoint

Descriptive statistics for SDAI, CDAI, DAS28-ESR, and DAS28-CRP at each assessment timepoint and their changes from baseline to each assessment timepoint will be calculated for each ARM (ARM-1, 2, and 3). Furthermore, analysis of covariance (ANCOVA) adjusted by country will be performed to compare changes from baseline to Week 48 between ARM-2 and ARM-3, and calculate the estimate of difference between the treatment arms and its two-tailed 95% confidence interval.

As a sensitivity analysis, point estimates and their 95% confidence interval for changes in measured values from baseline to each assessment timepoint will be calculated by generalized linear mixed model (Breslow NE, Clayton DG, J Am Stat Assoc 1993;88(421): 9-25, Wolfinger RD, O'Connell MA, J Stat Comput Sim 1993; 48: 233-243.). Unstructured will be selected as a correlation structure, and if the analysis does not converge, Toeplitz, Autoregressive, Compound-symmetry structure will be used in order.

6.2.6. Percentage of disease activity category by SDAI, CDAI, DAS28-ESR and DAS28-CRP at each assessment timepoint

The frequency of and the proportion of subjects classified into each disease activity category by SDAI, CDAI, DAS28-ESR and DAS28-CRP at each assessment timepoint will be calculated for each ARM (ARM-1, 2, or 3). Furthermore, Mantel-Haenszel test (risk difference) with country as a stratification factor will be performed to compare low disease activity and remission rate at each assessment timepoint between ARM-2 and ARM-3, and calculate the estimate of difference between the treatment arms and its two-tailed 95% confidence interval.

6.2.7. Tender joint count, swollen joint count, VAS (physician- and patient-reported), HAQ, CRP, ESR, MMP-3, RF, and anti-CCP antibody at each assessment timepoint, and change from baseline to each assessment timepoint

Descriptive statistics for tender joint count, swollen joint count, VAS (physician- and patient-reported), HAQ, CRP, ESR, MMP-3, RF, and anti-CCP antibody at each assessment timepoint and their changes from baseline to each assessment timepoint will be calculated for each ARM (ARM-1, 2, and 3). Furthermore, analysis of covariance (ANCOVA) adjusted by country will be performed to compare changes from baseline to Week 48 between ARM-2 and ARM-3, and calculate the estimate of difference between the treatment arms and its two-tailed 95% confidence interval.

6.2.8. Modified total sharp score (mTSS) at each assessment timepoint, and change from baseline to each assessment timepoint

Descriptive statistics for mTSS at each assessment timepoint and change from baseline to each assessment timepoint will be calculated for each ARM (ARM-1, 2, and 3). Furthermore, analysis of covariance (ANCOVA) adjusted by country will be performed to compare changes from baseline to Week 48 between ARM-2 and ARM-3, and calculate the estimate of difference between the treatment arms and its two-tailed 95% confidence interval. As with changes from baseline, descriptive statistics for changes from Week 24 to Week 48 will also be calculated for each ARM (ARM-1, 2, and 3). Furthermore, analysis of covariance (ANCOVA) adjusted by country will be performed to compare changes from Week 24 to Week 48 will also be calculated for each ARM (ARM-1, 2, and 3). Furthermore, analysis of covariance (ANCOVA) adjusted by country will be performed to compare changes from Week 24 to Week 48 between ARM-2 and ARM-3, and calculate the estimate of difference between the treatment arms and its two-tailed 95% confidence.

6.2.9. Structural remission (mTSS ≤0.5) rate at each assessment timepoint Structural remission rate and its two-tailed 95% confidence interval at each assessment timepoint will be calculated for each ARM (ARM-1, 2, and 3). Furthermore, Mantel-Haenszel test (risk difference) with country as a stratification factor will be performed to compare structural remission rates at Week 48 between ARM-2 and ARM-3, and calculate the estimate of difference between the treatment arms and its two-tailed 95% confidence interval.

7. Safety Analysis

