## 5.3 Withdrawal criteria

Subjects should be withdrawn from this study if applicable to any of the discontinuation criteria presented below. Upon withdrawal, subjects should undergo assessments and tests for early termination. Also, the reason for withdrawal should be as necessary explained to the subject, and treatment after withdrawal should be given in a faithful manner to ensure there will be no disadvantage to the subject.

Principal investigator/sub-investigator shall record the date of and reason for withdrawal in EDC. Also, for the traceable subjects, their clinical courses are followed up and reported to the Study Secretariat. Subjects withdrawn from this study do not need to be replaced regardless of the reason for withdrawal.

- 1) Subject wishes to discontinue his/her study treatment
- 2) Subject wishes to withdraw his/her consent
- 3) Serious (or significant) AE occurs, and the study treatment is determined to be difficult to continue
- 4) A comorbidity (complication, etc.) exacerbates, and the study treatment is determined to be difficult to continue
- 5) Definitive exacerbation of RA is confirmed
- 6) Use of bDMARDs other than ADA or use of JAK inhibitor
- 7) MTX at a dosage  $\geq 10$  mg/week cannot be maintained at Week 24 due to ADR, etc.
- 8) MTX at a specified dosage (ARM-2: 10 to 25 mg/week [the maximum dose should be set according to the package insert of each country], ARM-3: 6 to 8 mg/week) cannot be maintained after Week 24 due to ADR, etc.
- 9) An increased dosage of MTX is required after Week 24 due to loss of efficacy, etc.
- 10) Confirmed pregnancy
- 11) Confirmed critical protocol deviation
- 12) Found to be applicable to an exclusion criterion after enrollment in the study
- 13) Other reasons by which the study is not appropriate for continuation as judged by principal investigator/sub-investigator

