#### 9.6 Handling of study data

Subjects with missing data at an assessment timepoint of SDAI remission, ACR20, ACR50, and ACR70 response, HAQ remission, and structural remission due to study discontinuation or other relevant reasons will be considered as a "non-responder" at the specific timepoint. Any missing data on SDAI, CDAI, DAS28-ESR, and DAS28-CRP will be considered as missing at the specific timepoint. A missing data on the assessment of SDAI, CDAI, DAS28-

ESR, DAS28-CRP, and mTSS will be complemented with the last observation carried forward (LOCF).

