2.3. Handling of Study Data

- · Fixed data after the completion of follow-up will be used for statistical analyses.
- For subjects who were enrolled more than once, statistical analyses will be conducted by removing the data that became unnecessary.
- Data handling meeting will be held prior to the database lock to discuss and determine how to handle individual data after removing the information on which treatment arm each subject was randomized to.
- For clinical laboratory values that exceed or fall below detection limits, detection limits will be substituted for actual values.
- As a rule, baseline is defined as Week 0. If the value at Week 0 is missing or not measured, the time of screening is regarded as baseline.
- · Change and percentage change are defined as follows:

Change = measured value after intervention – measured value at baseline Percentage change = (change/measured value at baseline) x 100 (%)

- 2.4. Handling of Missing Values
 - Subjects with missing data at an assessment time point of SDAI remission, ACR20, ACR50, and ACR70 response, HAQ remission, and structural remission due to study discontinuation or other relevant reasons will be considered as a "non-responder" at the time point of missing data.
 - Subjects with missing data at an assessment time point of CDAI, DAS28-ESR, DAS28-CRP remission due to study discontinuation or other relevant reasons will be considered as a "non-responder" at the time point of missing data.
 - Any missing data on SDAI, CDAI, DAS28-ESR, and DAS28-CRP will be considered as missing at the time point of missing data.

If there is a missing data on the assessment of SDAI, CDAI, DAS28-ESR, DAS28-CRP, and mTSS, the sensitivity analysis of GEE or MMRM method will be performed. If the result does not converge, a missing data will be imputed with the last observation carried forward (LOCF). In addition, for the sensitivity analysis of primary endpoint, a missing data on the final scheduled visit will be imputed with data on End of Study.

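### The secondary Week 48 comparison of SDAI, CDAI and DAS28 appears to drop subjects withdrawn for flare, and the protocol and SAP give different missing-data rules for these scores

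*SAP*

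**What the plan says.** **Main comparison.** SAP 6.2.5, on SDAI, CDAI, DAS28-ESR and DAS28-CRP: "analysis of covariance (ANCOVA) adjusted by country will be performed to compare changes from baseline to Week 48 between ARM-2 and ARM-3".

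**Sensitivity analysis.** In the same section, "changes in measured values from baseline to each assessment timepoint will be calculated by generalized linear mixed model". It starts from an unstructured correlation, and "if the analysis does not converge, Toeplitz, Autoregressive, Compound-symmetry structure will be used in order". The sentence describes estimates of change and does not spell out an ARM-2 v ARM-3 contrast.

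**Missing scores, SAP 2.4.** "Any missing data on SDAI, CDAI, DAS28-ESR, and DAS28-CRP will be considered as missing at the time point of missing data". A GEE or MMRM sensitivity analysis follows, and then: "If the result does not converge, a missing data will be imputed with the last observation carried forward (LOCF". The End of Study value is brought in only for a sensitivity analysis of the primary endpoint.

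**Missing scores, Protocol 9.6.** "Any missing data on SDAI, CDAI, DAS28-ESR, and DAS28-CRP will be considered as missing at the specific timepoint". The next sentence begins its list with SDAI, CDAI and DAS28 and ends, with no condition attached: "ESR, DAS28-CRP, and mTSS will be complemented with the last observation carried forward (LOCF".

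**Withdrawal, Protocol 5.3.** The reasons include confirmed RA exacerbation and this one: "An increased dosage of MTX is required after Week 24 due to loss of efficacy, etc". Withdrawn subjects are to have early-termination assessments, and the schedule in Protocol 7.5 gives Week 48 and early termination a shared column.

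**Record of changes.** SAP 9.1 enters revisions from the protocol as not applicable.

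**The concern.** An ANCOVA on Week 48 change can use only subjects who have a Week 48 value. If missing scores stay missing, the subjects left out include some who were withdrawn because their arthritis worsened. Such withdrawal may also be uneven. ARM-2 stays at its maximum tolerable MTX dose while ARM-3 is reduced, and the trial is open-label, so needing more MTX could arise more often in ARM-3. Removing the worst courses from both arms, and more of them from the worse arm, draws the observed means together.

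The second problem is that the result depends on which text the analyst follows. The protocol's LOCF sentence and the SAP's rule that missing stays missing give different analysis populations and, as shown below, errors in opposite directions. What is at stake is the reading of the main continuous disease-activity results, which readers will set beside the remission rates when judging the reduced dose.

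**Working it through.** **1. Does the plan give a figure to reproduce?** Not for this comparison. Protocol 9.4.1 plans 110 subjects per arm for the primary test; that number serves here only as a group size. No SD for SDAI and no withdrawal rate after randomisation is stated, so everything below rests on assumptions.

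**2. Hand formula.** Let a share d2 of ARM-2 and d3 of ARM-3 be missing at Week 48, and suppose the missing subjects would have scored g points higher than those observed in their own arm. Each arm's true mean is its observed mean plus d × g, so

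true difference − observed difference = (d3 − d2) × g.

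- d2 = 5%, d3 = 10%, g = 10: 0.05 × 10 = 0.5 SDAI points.
- d2 = 10%, d3 = 20%, g = 15: 0.10 × 15 = 1.5 points.
- d2 = d3: zero.

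With a common g, the bias needs unequal loss. A real ARM-3 deficit produces unequal loss even under an identical rule, because more ARM-3 subjects cross the threshold.

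**3. Simulation.** Assumed: 110 per arm and 2,000 replicates. ARM-2 mean SDAI is 14, 9 and 8 at Weeks 24, 36 and 48, with ARM-3 higher by the true difference at Weeks 36 and 48. Correlations are 0.6 (Weeks 24–36), 0.7 (36–48) and 0.5 (24–48). After Week 36, 50% or 90% of subjects with SDAI above 18 are withdrawn, under the same rule in both arms. Entries in the last four columns are ARM-3 minus ARM-2 at Week 48.

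| True difference | SD | Withdrawn if above 18 | Lost, ARM-2 / ARM-3 | All subjects | Observed cases | LOCF | Likelihood |
|---|---|---|---|---|---|---|---|
| 2 | 8 | 50% | 7% / 10% | 1.97 | 1.78 | 2.08 | 1.98 |
| 2 | 8 | 90% | 12% / 17% | 2.02 | 1.59 | 2.21 | 2.03 |
| 2 | 10 | 50% | 9% / 12% | 1.95 | 1.77 | 2.06 | 1.97 |
| 2 | 10 | 90% | 17% / 22% | 2.05 | 1.57 | 2.22 | 2.04 |
| 4 | 8 | 50% | 7% / 13% | 3.97 | 3.56 | 4.18 | 3.97 |
| 4 | 8 | 90% | 12% / 24% | 4.03 | 3.04 | 4.40 | 4.01 |
| 4 | 10 | 50% | 9% / 15% | 3.99 | 3.55 | 4.18 | 3.99 |
| 4 | 10 | 90% | 17% / 28% | 4.00 | 2.95 | 4.34 | 4.01 |

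Observed cases understate by between 1 − 1.77/1.95 = 9% and 1 − 2.95/4.00 = 26%. LOCF overstates. With a true difference of 0, every rule returns a value within 0.05 of zero.

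The table compares Week 48 scores. Taking change from Week 0, when Week 0 and Week 36 are positively correlated, removes part of the shift, so the upper end is generous for the ANCOVA as planned.

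**4. Other assumed inputs, same rule in both arms.** With SD 7, a Week 36–48 correlation of 0.75, a cut-off of 14 and 50% or 80% withdrawn, observed cases give 1.78 or 1.53 for a true 2, and 3.53 or 3.07 for a true 4. That is 11 to 24% too low; the implied loss is about 6 to 23% in ARM-2 and 10 to 40% in ARM-3. Two further sets of runs gave 6 to 20% and 4 to 12%. The overall range is 4 to 26%.

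**5. Unequal withdrawal.** If 75% v 25%, or 80% v 40%, of those above the threshold are withdrawn in ARM-3 v ARM-2, a true deficit of 2 appears as 1.0 to 1.3. With no true difference, ARM-3 appears about 0.4 to 0.75 points better.

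**6. Against sampling error.** With everyone observed, the standard error is SD × √(2/110) = SD × 0.135, or 0.94 at SD 7 and 1.35 at SD 10. The equal-rule shifts in the table, 0.18 to 1.05 points, are all smaller than the matching standard error.

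**The case against.** - **Non-inferiority.** A reader might infer that this pulls the non-inferiority conclusion towards success. The documents do not support that. The margin applies only to the SDAI remission rate (Protocol 9.2.1.1, SAP 6.1), where a missing result counts as non-response. SAP 6.2.5 has no margin and uses a 95% interval.
- **Completers only.** No sentence says so; it is inferred from SAP 2.4. The shared Week 48 or early-termination column could be read as supplying a score, and under Protocol 9.6 LOCF the error runs the other way. The documents therefore do not fix the direction of bias. This stands, and it is itself a reason to settle the rule.
- **Three incompatible rules.** SAP 2.4 can be read as a sequence: missing in the main analysis, a model as sensitivity, LOCF if the model fails. The covariance ladder in SAP 6.2.5 can be fitted in before LOCF. The clear conflicts are within Protocol 9.6 and between it and the SAP.
- **Mixed withdrawal reasons.** Protocol 5.3 also covers adverse events, comorbidity and the subject's own wish, which need not track SDAI. This stands; the simulations model flare only.
- **Remedy already planned.** Largely true, but as a sensitivity analysis without a stated arm contrast.
- **The simulation favours the mixed model.** Withdrawal there depends on a recorded score. When it was made to depend on an unrecorded value between Weeks 36 and 48, the likelihood estimate was also low: 1.75 to 1.94 for a true 2, and 3.6 to 3.85 for a true 4.
- **mTSS.** A reader might object that LOCF sets the Week 24–48 change to zero while the same subject counts as a structural-remission failure. Protocol 7.2.1 requires an early-termination film unless the last was within 28 days, so this mainly concerns exits soon after Week 24 and is minor.

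**Conclusion.** The point holds for a secondary comparison, at moderate weight. On the most natural reading of the SAP, the main Week 48 analysis of the four indices leaves out subjects withdrawn for worsening disease, and the protocol prescribes something different without SAP 9.1 recording it. If ARM-3 is truly worse, and one withdrawal rule acts in both arms, the understatement is roughly 4 to 26% under SDs of 7 to 10 and losses of about 6 to 40% per arm. It is larger if ARM-3 subjects are withdrawn more readily, and absent if the true difference is zero and withdrawal is equal. LOCF tends to overstate the deficit. The percentages are illustrations from assumed inputs, not forecasts for this trial. The conflict between the documents does not depend on them.

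**What to change.** 1. In SAP 6.2.5, make the repeated-measures mixed model the main Week 48 comparison. State the ARM-3 minus ARM-2 contrast with its 95% interval, and use a likelihood-based model rather than leaving the choice of GEE or MMRM open. Keep the observed-case ANCOVA as supportive.
2. State that early-termination scores are mapped to the nearest scheduled visit, so that a recorded flare enters the model.
3. Keep one convergence rule, the covariance ladder in SAP 6.2.5. Remove LOCF from Protocol 9.6 and SAP 2.4, or label it as sensitivity only.
4. Record the change in SAP 9.1. The same edit should settle the comparison window: Protocol 9.2.1.2 compares change from Week 24 to Week 48, SAP 6.2.5 change from baseline.

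The cost is wording in two documents and modest programming for a model that is already planned. The downside is reliance on missing-at-random: withdrawal driven by a flare that no score records would still leave some bias, so reasons for missing Week 48 scores should be tabulated by arm.
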